4.7 Subgroup analyses

Descriptive statistics of the following subgroups shall be presented summarised by PAD vs. without PAD and overall:

- Disease severity
 - graded clinically according to the severity of symptoms (from least to worst severe; asymptomatic, intermittent claudication, rest pain and tissue loss).
 - Measured radiologically using the ANGIO-score (categorised as mild (≤ 4); moderate (5-9); severe (≥ 10)).
- Presence vs. absence of neuropathy at presentation.
- Presence vs. absence of diabetic foot ulcer (DFU) at presentation.
- Age groups (i.e. ≤ 59 years; 60 – 69 years; 70 – 79 years; ≥ 80 years).

Note that pre-specified subgroup analyses will be unlikely to be adequately powered and so no formal statistical analysis will be performed here and table shall be used for descriptive purposes.

5. Validation and QC

Data collection and quality checks will be carried in accordance to SOP ECTU_DM_01. A second statistician will perform separate programming and checking of primary outcome results and conclusions. The statistical report will also be read and sense-checked.

6. Data sharing

A file, or set of files, containing the final data will be prepared, along with a data dictionary. These will be made available to the Chief Investigator at the end of the analysis phase.

7. References

- [1] SAS® Institute Inc. SAS for Windows. SAS Institute Inc.: Cary, NC, U.S.A
- [2] *Pepe and Thomson (Biostatistics, 2000; 1, 2; 123-140 'Combining diagnostic test results to increase accuracy')*
- [3] Little RJ, D'Agostino R, Cohen ML, Dickersin K, Emerson SS, Farrar JT et al. The prevention and treatment of missing data in clinical trials. *N Engl J Med*; 367:1355-60.

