2.2 Secondary Objective

- To determine the cost-effectiveness of tests over a time horizon of 5 years
- To determine the performance of tests using exploratory diagnostic thresholds
- To explore the effect of combining different tests on diagnostic performance
- To evaluate patient acceptability of tests
- To evaluate the effect of confounding patient characteristics (e.g., neuropathy and ulceration) on diagnostic performance
- To evaluate the performance of tests for establishing the severity of PAD
- To evaluate inter- and intra-rater reliability of tests
- To evaluate the performance of PAD-scan (in selected centres).

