8.4 Statistical Analysis

The five individual tests (and the sixth exploratory test in four sites) will be compared against the reference test (CTA/MRA), calculating standard diagnostic accuracy metrics of sensitivity, specificity, predictive values, likelihood ratio, and diagnostic odds ratio (using the bivariate model approach implemented in R). 95% confidence intervals calculated at 99% to adjust for the five comparisons will be presented. The robustness of the findings to any observed patterns of missing data will be assessed, which are expected to differ by test. A multiple imputation approach will be used assuming the data are missing at random. In addition, and probably more consistent with the likely missing data generating mechanisms, sensitivity type analyses assuming the data are missing not at random (i.e. informatively missing) will be explored. This would attempt to identify different types of missing data by an underlying reason or reasons, and then imputing values that capture plausible measurements for those missing data. The ?-adjustment approach given by van Buuren will be followed ([Flexible Imputation of Missing Data, Chapman and Hall, 2018, section 3.8ff](#)), and also the recommendations of Molenberghs & Kenward ([Missing Data in Clinical Studies, Wiley, 2007; Section 19ff on sensitivity analyses](#)). These approaches would allow the set of reasons for missing values to vary across the tests. The purpose is to stress the calculated findings to test their robustness to the observed patterns of missing data.

The subgroups of disease severity (both clinically and radiologically defined as detailed below) will be explored and those with/without neuropathy or DFU. The subgroups in the Statistical Analysis Plan will be pre-specified. Any further subgroup analysis (e.g. if suggested later by new data external to the study) will be labelled exploratory. Pre-specified subgroup analyses will be unlikely to be adequately powered. Clinical severity will be graded according to the severity of symptoms (from least to most severe; asymptomatic, intermittent claudication, rest pain and tissue loss). Severity will be measured radiologically using the ANGIO-score as outlined in section 5.7. Both will be analysed as pre-specified subgroup analyses in the Statistical Analysis Plan.

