3.1 SAP objectives

The objective of this SAP is to describe the statistical analyses contributing to the final report and publication(s) of the DM PAD study. All analyses detailed in the study protocol are addressed with the exception of the internal pilot of the study which will be documented separately.

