3.3 General

In general terms, categorical data will be presented using counts and percentages, whilst continuous variables will be presented using the mean, median, standard deviation (SD), minimum, maximum, Q1, Q3, inter-quartile range (IQR) and number of patients with an observation (n).

The comparison group here is diagnostic technique, so where applicable results will be split by diagnostic tests.

A further reporting metric is the number of participants who were included in the analysis, which will be supported for each of the primary (section 4.4) and secondary (section 4.5) analyses by the preparation of a STARD-style flow chart showing the 'pipeline leakage' from participants who were enrolled, to participants included in the analysis.

Where there is missing data for an outcome variable, in the first instance, those individual cases will be removed from any statistical analysis relating to that outcome variable (i.e. complete case analysis), unless otherwise specified. In tabulations, numbers of missing observations will be provided, but percentages will not include them.

All analysis and data manipulation will be carried out using SAS [1] unless otherwise stated.

Qualitative or health economic analysis will not be covered by this SAP. However, data from the statistics report may be used for health economics analyses.

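### SAP 4.7 tabulates subgroups by PAD status and names no index-test performance, so two secondary objectives have no explicit analysis

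*SAP*

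**What the plan says.** Protocol 2.2 lists two secondary objectives about how the tests perform: "To evaluate the effect of confounding patient characteristics (e.g., neuropathy and ulceration) on diagnostic performance" and "To evaluate the performance of tests for establishing the severity of PAD".

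Protocol 8.4, repeated in SAP section 2, says: "The subgroups of disease severity (both clinically and radiologically defined as detailed below) will be explored and those with/without neuropathy or DFU". Of the clinical and radiological severity gradings it adds: "Both will be analysed as pre-specified subgroup analyses in the Statistical Analysis Plan". It names no measure or method for these subgroups.

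SAP 4.7 is where the analysis is set out. It says "Descriptive statistics of the following subgroups shall be presented summarised by PAD vs. without PAD and overall" and lists symptom grade, ANGIO band, neuropathy, DFU and age group. It notes that power is unlikely to be adequate, "so no formal statistical analysis will be performed here and table shall be used for descriptive purposes".

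Two general statements also bear on the point. SAP 3.1 says: "All analyses detailed in the study protocol are addressed with the exception of the internal pilot". SAP 3.3 says: "The comparison group here is diagnostic technique, so where applicable results will be split by diagnostic tests".

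**The concern.** Both objectives ask about the performance of an index test: whether it changes with neuropathy or ulceration, and whether the test can grade severity. The table in SAP 4.7 has subgroups as rows and PAD status as columns. It names no index test, no sensitivity or specificity, no interval, and no test result by severity band. It shows how often PAD occurs in each subgroup, which is a different question.

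The consequence differs between the two objectives. For neuropathy and DFU, the strata, thresholds and accuracy measures are fixed elsewhere, so little is open beyond the cross-tabulation and the confidence level. For severity no method is named anywhere, so one could be chosen after the results are seen.

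**Working it through.** **1. Does another SAP section supply the analysis?**

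| SAP section | What it covers | By neuropathy, DFU or symptoms? | Test result by ANGIO band? |
|---|---|---|---|
| 4.3 | Test scores by reference standard, overall and by site | No | No |
| 4.4 | Sensitivity, ROC cut-points | No | No |
| 4.5 | Specificity and related measures, reliability, test combinations | No | No |
| 4.6 | Missing data | No | No |
| 4.7 | Subgroups by PAD, without PAD, overall | Frequencies only | No |

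**2. Inputs.** Protocol 8.1 gives 255 participants with PAD and 255 without. The 255 reproduces: an exact one-sided binomial test at 1%, of 90% sensitivity against 90 − 8.2 = 81.8%, keeps at least 90% power from n = 255 upwards (92.4% at 255). For 80% against 69.8% the figure is 253 (90.7% at 255).

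The documents do not give the DFU share among PAD cases. The only DFU figure is 40%, from the hospital foot-clinic cohort in the protocol's cost-effectiveness background, where PAD prevalence was 66%. Recruitment from primary care could lower the share in this study. The protocol's statement that PAD is a key risk factor for ulceration could raise it among PAD cases. I assume 40% and show 20% to 60%.

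**3. What the table can show.** At 40%, 255 × 0.40 = 102 PAD cases have DFU and 153 do not. With 80% overall sensitivity there are 0.80 × 255 = 204 true positives (expected counts below):

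| Sensitivity, DFU | Sensitivity, no DFU | True positives | SAP 4.7 PAD column |
|---|---|---|---|
| 95% | 70% | 96.9 + 107.1 = 204 | 102 / 153 |
| 80% | 80% | 81.6 + 122.4 = 204 | 102 / 153 |
| 65% | 90% | 66.3 + 137.7 = 204 | 102 / 153 |

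Three quite different answers to the objective give the same table.

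**4. The ANGIO rows.** Under SAP 3.5 a leg without PAD has total score 0. All 255 such legs therefore fall in the mild band (≤4), and the without-PAD column reads 255 / 0 / 0 by definition. The PAD column is unaffected. The overall column mixes those legs with mild PAD.

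**5. Precision if sensitivity were reported.** Wald half-width = z × √(0.8 × 0.2 / n), z = 1.960 (95%) or 2.576 (99%), every test completed:

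| Assumed DFU share | n with PAD and DFU | 95% | 99% |
|---|---|---|---|
| 20% | 51 | 11.0 | 14.4 |
| 40% | 102 | 7.8 | 10.2 |
| 60% | 153 | 6.3 | 8.3 |

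At a 40% share the no-DFU group (n = 153) has 6.3 and 8.3 points. The 10.2 in the table only coincides with the 10.2% in protocol 8.1, which is the margin in the power calculation reproduced in step 2.

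Incomplete tests widen these intervals. If 20% lack a TBPI, as in the TrEAD study, 7.8 becomes 7.8 / √0.8 = 8.7 points.

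**6. Power of a formal comparison.** For 80% against 70% sensitivity between DFU and no DFU, two-sided 5%, power is 28%, 37%, 43% and 45% at DFU shares of 20%, 30%, 40% and 50%.

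**The case against.** The best case for the plan has four parts.

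- **Exploring can be descriptive.** Protocol 8.4 names no metric, and both documents concede low power. This stands. A reader might infer that SAP 4.7 contradicts protocol 8.4, or that the completeness statement in SAP 3.1 is false. The documents do not support either reading: 8.4 sets out no subgroup accuracy analysis, and 4.7 does list both severity gradings. The gap lies between 4.7 and the objectives in 2.2.
- **SAP 3.3 may already cover it.** SAP 4.7 does not say which variable is described. If index-test results were split by test and by PAD status within each subgroup, sensitivity and specificity would follow. That reading is possible, but 3.3 is a general rule limited to where it applies, it names no accuracy measure, and 4.7 sets its own columns. It does not make the analysis explicit.
- **Little is left to choose for neuropathy and DFU.** This stands and limits the consequence for that objective. It does not help the severity objective.
- **The ANGIO bands are already split by PAD status.** This stands for the PAD column. Only the overall column mixes score-0 legs into the mild band.

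Low power is a fair reason to avoid hypothesis tests, as step 6 shows. It is no reason to leave out estimates with intervals.

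**Conclusion.** The point holds in a limited form. Two of eight secondary objectives have no explicit analysis, and the table specified in SAP 4.7, read as written, cannot answer either of them. The choice of a descriptive approach is sound; what is described is the problem. The specification of the primary endpoint is not affected, so this is an amendment that should be made, not a threat to the main result.

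A reader might also infer that the sponsor has dropped these objectives. Nothing in the SAP says so.

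That the table cannot show performance does not depend on the assumed DFU share. The half-widths do: they rest on 255 PAD cases, 80% sensitivity, completed tests and a DFU share that the documents do not give.

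**What to change.** Amend SAP 4.7, before accuracy results are seen, to report for each index test, labelled exploratory and without hypothesis tests:

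1. Sensitivity and specificity with denominators and confidence intervals, by neuropathy, DFU and symptom grade. State one confidence level, consistent with the main analysis (protocol 8.4 and SAP section 2 calculate those intervals at 99%).
2. Sensitivity by ANGIO band (mild, moderate, severe) among PAD-positive assessed legs. Keep score-0 legs without PAD out of the mild band in the overall column.
3. For the severity objective, index-test results by ANGIO band among PAD-positive legs: the distribution for ABPI, TBPI and exercise ABPI, and the proportion positive for the waveform tests (the same figure as in item 2 for those tests). Give any AUC a dichotomy stated in advance, for example ANGIO ≥5 against ≤4, or leave it out.

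Item 2 shows how well PAD is detected at each severity; only item 3 addresses how well a test grades it. If the sponsor does not intend these analyses, the SAP should say that the objectives will not be analysed.

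**Cost.** SAP wording and tables from data already collected. For five tests there are 5 × 8 levels (neuropathy 2, DFU 2, symptom grade 4) × 2 measures = 80 estimates, plus 5 × 3 bands = 15, about 95 in all, before the distributions in item 3. Many will be imprecise and should be presented as such.

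**Separate matter.** Protocol 5.8 counts tandem lesions as PAD on their combined stenosis, while SAP 3.5 defines PAD by the total score alone. That affects the reference standard for the primary endpoint and should be reconciled as a finding of its own.
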